13.5 Use of Information

All personal data pertaining to the subjects in this study and in any subsequent reports will be kept confidential. Subjects will be identified only by their month and year of birth and a subject number. It is the responsibility of the Investigator to keep a subject listing for cross-referencing.

The sponsor will notify the Member States concerned about a serious data security breach at the time of the breach without undue delay but not later than 7 days of becoming aware of that breach. Measures that will be implemented to mitigate the possible adverse effects of a serious data security breach include, but are not limited to, back-ups including remote location, high availability systems for critical environments, and a security incident response plan.

The Investigator understands that the information developed in the clinical study will be used by the Sponsor in connection with the development of the study drug. This information may be disclosed to other clinical Investigators, to the US FDA, and to other government agencies.

The Sponsor will ensure that personal data transfers and bodily materials transfer comply with Data Protection Laws of the EU, i.e., the [General Data Protection Regulation 2016/679](#). To that end, all parties/vendors involved in this study will have been assessed and qualified by the Sponsor to ensure data privacy protection is at an adequate level. Appropriate contractual arrangements (Standard Contractual Clauses) will be in place and sufficient supplement technical measures will be implemented by the parties involved in the study.

13.6 End of Study and Final Report

The end of the study is defined as the date of the last visit of the last subject in the study globally.

The Investigator or delegate must notify the IRB/EC upon study completion or termination in compliance with local regulations.

The Sponsor or its designee will provide a final report and/or synopsis to the Investigators, the IRB/EC and Regulatory Authorities in accordance with local requirements.

13.7 Financing and Insurance

Financing and Insurance are addressed separately in the Clinical Study Agreement.

13.8 Publication Policy

Publication policy is addressed separately in the Clinical Study Agreement.

Reporting of clinical study results will be performed in accordance with local Competent Authority regulatory requirements and obligations (e.g., trial data uploaded to EudraCT database within one year following end of the trial).

15.0 PROTOCOL SUMMARY OF CHANGES

16.0 APPENDICES

16.2 Appendix 2: Clinical Laboratory Tests

Chemistry	Hematology
Sodium	Hematocrit
Potassium	Hemoglobin
Chloride	Red blood cells
Bicarbonate	White blood cells (WBCs)
Blood urea nitrogen (BUN)	Neutrophils
Creatinine	Lymphocytes
Glucose	Monocytes
Calcium	Eosinophils
Phosphorus	Basophils
Albumin	Platelets
Total protein	
Alkaline phosphatase (ALP)	
Aspartate aminotransferase (AST)	
Alanine aminotransferase (ALT)	
Gamma-glutamyl transferase (γ GT)	
Total and direct bilirubin	
Lactic dehydrogenase (LDH)	
Creatinine clearance (eGFR by CKD-EPI or Bedside Schwartz)*	
C-reactive protein (CRP)	
Other Tests	Coagulation
Pregnancy testing	INR
	Prothrombin time

* Estimated glomerular filtration rate (eGFR) is to be calculated using the CKD-Chronic Kidney Disease Epidemiology Collaboration (CKD-EPI) Creatinine Equation 2009 calculation for calculation for adult subjects and Bedside Schwartz equation, according to the recommendation from National Institutes of Health/National Institute of Diabetes and Digestive and Kidney Diseases, for pediatric subjects.

## **MODIFICATION HISTORY**

Current Version	Date	Amended by	Summary of Changes from Previous Version	Reason
1.0	03-Nov-2022	N/A	Original document	N/A

## 1. ABBREVIATIONS

Abbreviation	Definition
AD	Analysis Description
AE	Adverse Events
AESI	Adverse Event of Special Interest
BCVA	Best Corrected Visual Acuity
CE	Contralateral Eye
CSR	Clinical Study Report
ETDRS	Early Treatment Diabetic Retinopathy Study
FST	Full-field Stimulus Testing
ICF	Informed Consent Form
ICH	International Council on Harmonization
IRT	Interactive Response Technology
IVT	Intravitreal
LLVA	Low Luminance Visual Acuity
MedDRA	Medical Dictionary for Regulatory Activities
MH	Medical History
PT	Preferred Term
RP	Retinitis Pigmentosa
RTF	Rich Text Format
SAE	Serious Adverse Event
SAP	Statistical Analysis Plan
SD-OCT	Spectral Domain Optical Coherence Tomography
SOC	System Organ Class
TE	Treated Eye
TEAE	Treatment Emergent Adverse Event
TLF	Table Listing Figure format
WHO	World Health Organization

## **2. INTRODUCTION AND STUDY OBJECTIVES**

### **2.1. Introduction**

Study PQ-421a-003 (Sirius) aimed to define safety and quantify the treatment effect of ultevursen administered via intravitreal (IVT) injection in subjects with retinitis pigmentosa (RP) due to mutations in exon 13 of the *USH2A* gene, relative to masked, untreated sham-control subjects, at 2 dose regimens of ultevursen.

### **2.2. Study Termination**

In this context, the Analysis Description (AD) is abbreviated and describes the populations for analysis, data handling rules, statistical methods, and formats for data presentation that will be required for the close out of the study, after all randomized subjects have completed the end of study visit and the database is locked.

The summary tabulations and listings that will be produced for the close out of the study, will provide the basis for the appropriate sections of the abbreviated clinical study report (CSR) or equivalent document.

### **3. STUDY DESIGN**

#### **3.1. Synopsis of Study Design**

PQ-421a-003 is a double-masked, randomized, controlled, multiple-dose study to evaluate the efficacy, safety and tolerability of ultevursen in subjects with RP due to mutations in exon 13 of the *USH2A* gene.

At study start, subjects are randomized to one of the following treatment groups:

- Group 1: Ultевурсен 180/60 μg (180 μg loading dose administered on Day 1, 60 μg maintenance dose administered at Month 3, and every 6 months thereafter; n = 27)
- Group 2: Ultевурсен 60/60 μg (60 μg loading dose administered on Day 1, 60 μg maintenance dose administered at Month 3, and every 6 months thereafter; n = 27)
- Group 3: Sham-procedure (administered on Day 1, Month 3, and every 6 months thereafter; n = 27)

Please refer to Section 4.2 of the study protocol for details regarding the study design.

#### **3.2. Randomization Methodology**

The randomization procedure used to assign study treatment to eligible subjects/eye was through a centralized Interactive Response Technology (IRT), utilizing the randomization schedule generated by the designated unmasked statistician.

Two periods of randomization were planned:

Subjects who satisfy all eligibility criteria at Day 1 were randomized in a 1:1:1 ratio to one of the following groups:

- Ultевурсен 180/60 μg
- Ultевурсен 60/60 μg
- Sham-procedure

The randomization in both periods was stratified at Day 1 on one single factor, collected during the Day 1 visit: Syndromic subjects versus Non-Syndromic subjects.

### **3.3. Study Procedures**

Please refer to Section 8.0 of the study protocol for details regarding the study procedures.

### **3.4. Unmasking**

#### **4. POPULATIONS DEFINITIONS**

The following analysis sets will be evaluated and used for presentation and analysis of the data.

Analysis sets defined by eye will be respect to each eye. For example, the Safety Analysis Set for the CE will be determined by measurements taken on the CE. The subject-level analysis sets consist of subjects who meet the criteria in at least one of the eye-level analysis sets.

**Screening Analysis Set:** Includes all subjects who signed the informed consent form.

**Safety Analysis Set (SAF):** All screened subjects who were randomized and received at least one dose of study treatment.

The disposition data will be presented for all screened subjects. The SAF will be the primary set for the analysis of the safety parameters. The SAF will also be used for descriptive summaries of demographics, baseline characteristics, and ocular/non-ocular medical history.

## **5. STATISTICAL METHODS**

### **5.1. Computing Environment**

All information and analyses in the tables and listings provided will be performed using SAS statistical software Version 9.4 or later, unless otherwise noted. The Medical History (MH) and Adverse Events (AEs) will be coded using Medical Dictionary for Regulatory Activities (MedDRA) version 24.1. The Prior and Concomitant Medications will be coded using World Health Organization (WHO) Drug version Global B3 September 2021.

### **5.2. Definition of Baseline**

Baseline BCVA for the TE is defined as the mean of all BCVA assessments collected during the screening period.

Baseline BCVA for the CE is defined as the mean of all BCVA assessments collected during the screening period.

### **5.3. Data Handling**

#### **5.3.1. General**

Unless otherwise noted, the data reported in the listings will be as reported on the electronic case report form.

### **5.4. General Statistical Methods**

All output will be incorporated into Rich Text Format (RTF) files and bookmarked PDFs, sorted and labeled according to the International Conference on Harmonisation (ICH) recommendations, and formatted to the appropriate page size(s).

Tabulations will be produced for appropriate disposition and demographic characteristics.

For measurements of continuous variables, summary statistics of absolute values will be reported and will include n, mean, standard deviation, median, and minimum and maximum values. The number of missing values will be displayed in parenthesis next to 'n'. Mean, standard deviation, median, will be presented with one more decimal place compared to the raw data, and minimum and maximum will be presented with the same number of decimal places as the raw data.

For categorical variables, summary tabulations of the number and percentage within each category of the parameter will be presented (as well as the number for missing data).

Denominator for percentages is column N. Percentages will be rounded to one decimal place.

Therefore, there may be cases where for instance the total of the percentages does not exactly equal 100%.

Where appropriate, data will be listed by eye (i.e., TE, CE).

In summary tables the study treatments will be presented in the following order: 'Ultevursen 180/60 µg', 'Ultevursen 60/60 µg', and 'All Subjects'.

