## **5.5. Study Population**

### **5.5.1. Subject Disposition**

Subject disposition, including the number of screened subjects, the number of subjects failed screening, the number of randomized subjects, the number of subjects who received study treatment in the TE, the number of subjects who received study treatment in the CE, who completed the study and the number of subjects who discontinued from the study, along with the reasons will be summarized by treatment group.

A listing of subject disposition will be generated, including the reason for premature study or treatment discontinuation, if applicable.

A listing of screen failure data will also be provided.

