### **5.5.2. Demographic and Baseline Characteristics**

Demographic and baseline characteristics, including age as collected, age category (Adult  $\geq$ 18 years, Children  $<$ 18 years), gender, race, ethnicity, body weight (kg), height (cm), genotype (homozygous, heterozygous), and baseline BCVA (ETDRS letter score for both TE and CE), will be summarized for the Safety Population by treatment group using descriptive statistics.

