## **5.6. Safety – Adverse events**

A treatment-emergent AE (TEAE) is defined as an event that was not present prior to administration of the dose of study drug (ultevursen or sham-procedure) and present after the dose or if it represents the exacerbation of an event that was present prior to the dose.

Adverse events will be summarized by treatment group separately as follows:

- For non-ocular AE:
  - by subject, therefore, in any tabulation, a subject contributes only once to the count for a given adverse event (System Organ Class [SOC] or Preferred Term [PT])
  - and during the overall study period (i.e., up to the last visit for the last subject).

- Time to onset will be calculated in hours, relative to the last dose received, irrespective of which eye received the last dose (i.e., TE or CE).
- For ocular AE:
  - by eye frequencies, separately for the TE and the CE, therefore, in any tabulation, an eye contributes only once to the count for a given AE (by SOC or PT). AEs that are reported in both eyes (i.e., OU) will be reported individually by eye in the tabular summaries.
  - and during the overall study period (i.e., up to the last visit for the last subject).
  - Time to onset will be calculated in hours, relative to the last dose received in the eye experiencing the ocular AE.

Unless otherwise stated, any summary of any type of TEAEs which includes the SOC and PT of the events will order the SOC and the PTs within the SOC by descending incidence of PT.

The following summary tables will be produced separately according to the type of AEs (ocular/non-ocular where applicable) as defined above:

- Overview of Ocular Adverse Events for Treatment Eye during the overall study period (Safety Population)
- Overview of Ocular Adverse Events for Contralateral Eye during the overall study period (Safety Population)
- Overview of Non-Ocular Adverse Events during the overall study period (Safety Population)
- Summary of Ocular Treatment-Emergent Adverse Events for Treatment Eye during the overall study period by MedDRA System Organ Class and Preferred Term (Safety Population)
- Summary of Ocular Treatment-Emergent Adverse Events for Contralateral Eye during the overall study period by MedDRA System Organ Class and Preferred Term (Safety Population).
- SAEs
- AESIs

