## **6. CHANGES TO PLANNED ANALYSES**

As the study is prematurely stopped by Sponsor's decision, no formal statistical analysis will be produced. Only disposition, demographic and baseline characteristics, and overview of AEs will be summarized in tables. By-subjects data listings will be produced based on raw data.

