## **8. APPENDICES**

The shells of planned outputs are provided in a separate document (PQ-421a-003\_List of Planned Outputs\_Final\_V1.0 (2022-11-03)).

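### SAP 5.4 leaves the randomized sham arm out of the summary-table columns, against the by-treatment-group instructions in SAP 5.5 and 5.6

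*SAP*

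**What the plan says.** SAP 5.4 states the layout rule for summary tables: "In summary tables the study treatments will be presented in the following order: 'Ultevursen 180/60 µg', 'Ultevursen 60/60 µg', and 'All Subjects". The list ends there, with 'and' before its last item and no visible gap in the sentence.

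Elsewhere the sham arm is a full treatment group:

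- SAP 3.1 lists it beside the two ultevursen regimens: "Group 3: Sham-procedure (administered on Day 1, Month 3, and every 6 months thereafter; n = 27".
- SAP 3.2 says that subjects "were randomized in a 1:1:1 ratio to one of the following groups", and sham is the third group named.
- SAP 5.5.1, on disposition: "along with the reasons will be summarized by treatment group".
- SAP 5.5.2, on demographics and baseline: "will be summarized for the Safety Population by treatment group using descriptive statistics".
- SAP 5.6: "Adverse events will be summarized by treatment group separately as follows". The definition of a treatment-emergent event in that section counts the sham procedure as study drug.
- SAP 4 defines the Safety Analysis Set by randomization and at least one dose of study treatment, with no exclusion of sham.

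Protocol 10.6 calls for baseline data by treatment group and also pooled over all subjects. Protocol 10.9.1 calls for treatment-emergent events by treatment group.

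SAP 6 limits what is tabulated after the early stop: "Only disposition, demographic and baseline characteristics, and overview of AEs will be summarized in tables". It declares no removal of the control column. On the table layouts, SAP 8 says: "The shells of planned outputs are provided in a separate document".

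**The concern.** The column list and the by-treatment-group instructions cannot both be followed. Three treatment groups plus a total make four columns, and SAP 5.4 lists three. Section 6 is where the SAP declares its changes, and it gives only the early stop and the absence of formal analysis.

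The tables that remain are the only planned summaries of this trial. Without a sham column, a reader could not set adverse-event frequencies or baseline characteristics in the ultevursen arms beside those of the concurrent control. SAP 2.1 describes the study's aim as relative to sham-control subjects. Because SAP 5.4 uses the column N as the denominator for percentages, no sham denominator or percentage would be printed either. The by-subject listings in SAP 5.7 hold the individual records but give no summary of the control arm.

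**Working it through.** **Inputs.** Planned arm sizes 27, 27 and 27 (SAP 3.1); planned total about 81 (Protocol synopsis); column list and one-extra-decimal rule for means (SAP 5.4); table items (SAP 5.5.1, 5.5.2, 5.6 and 6).

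**Planned total.** 27 + 27 + 27 = 81, which agrees with the synopsis.

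**Subjects without their own column.** The two listed treatment columns hold 27 + 27 = 54. The remainder is 81 − 54 = 27, and 27/81 = 33.3%.

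**Tables governed by the list.** The SAP names 1 disposition item (5.5.1), 1 baseline item (5.5.2) and 7 adverse-event bullets (5.6): 1 + 1 + 7 = 9. If 'overview' in SAP 6 is read strictly, only the 3 overview tables in 5.6 survive: 1 + 1 + 3 = 5. All of them fall under 5.4 on either count.

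**What a reader could recover.** Suppose that 'All Subjects' is the sum of the three arms. The SAP does not define it.

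- *Counts:* sham = All − (180/60) − (60/60), exact. The sham denominator follows in the same way.
- *Means:* with equal arms, sham mean = 3 × All − (180/60) − (60/60). For integer raw data, means are shown to one decimal, so each is rounded by at most 0.05. The worst error is 3 × 0.05 + 0.05 + 0.05 = 0.25.
- *Medians:* not determined in general by the pooled and the two active medians.
- *Minimum or maximum:* visible only when the overall extreme lies beyond both active arms, so that it must belong to sham. If the arms are exchangeable and equal in size, the chance is at most 27/81 = 1/3 for each.

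**Where the assumption may fail.** SAP 4 presents disposition for all screened subjects. The total column of that table could therefore include screen failures, and subtraction would then work only for rows confined to randomized subjects.

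**The case against.** The strongest reply is that SAP 5.4 sets an order and does not decide which arms are tabulated. Content is set by 5.5.1, 5.5.2 and 5.6, and a programmer who follows those sections would produce a sham column. The shells may already contain one. No formal analysis is planned, listings cover every treated subject, and the repair is one term.

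Much of this is fair. Harm in the produced tables is not shown, and the omission is probably clerical. The figure of 9 items needs the lower reading of 5 beside it. The 0.25 bound does not carry over to every variable: baseline BCVA is a mean of screening assessments (SAP 5.2) and need not be an integer, and actual arm sizes may be unequal. The public copy also lacks some text around study termination (SAP 2.2) and unmasking (SAP 3.4), so one can say only that the visible text gives no reason for the omission.

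None of this makes the list correct. An ordering rule that names two of three arms and a total is incomplete as an ordering rule as well, and it is the general rule for all summary tables. Masking does not explain the gap in the visible text: SAP 2.2 places the outputs after database lock, and the two active regimens are shown separately.

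**Conclusion.** The concern holds. SAP 5.4 omits the randomized control from the summary-table columns and contradicts SAP 3.1, 3.2, 5.5.1, 5.5.2 and 5.6, as well as Protocol 10.6 and 10.9.1. It should be fixed, because it governs the only summaries that remain.

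The size is one of three arms, on planned rather than actual numbers. The recovery figures are illustrations that depend on equal arms, integer raw data, exchangeability and a total that is the sum of the arms. The consequence is confined to descriptive reporting of disposition, baseline and safety. Whether the produced tables lack sham depends on shells that were not available for this review.

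**What to change.** Change the column list in SAP 5.4 to four entries: 'Ultevursen 180/60 µg', 'Ultevursen 60/60 µg', 'Sham-procedure' and 'All Subjects'. State what 'All Subjects' contains, in particular whether it includes screen failures in the disposition table. Then confirm that the separate output shells match. A pooled ultevursen column is optional.

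The cost is a small edit to SAP 5.4 and a check of the shells. No new data are needed.

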## **5.5. Study Population**

### **5.5.1. Subject Disposition**

Subject disposition, including the number of screened subjects, the number of subjects failed screening, the number of randomized subjects, the number of subjects who received study treatment in the TE, the number of subjects who received study treatment in the CE, who completed the study and the number of subjects who discontinued from the study, along with the reasons will be summarized by treatment group.

A listing of subject disposition will be generated, including the reason for premature study or treatment discontinuation, if applicable.

A listing of screen failure data will also be provided.

### **5.5.2. Demographic and Baseline Characteristics**

Demographic and baseline characteristics, including age as collected, age category (Adult  $\geq$ 18 years, Children  $<$ 18 years), gender, race, ethnicity, body weight (kg), height (cm), genotype (homozygous, heterozygous), and baseline BCVA (ETDRS letter score for both TE and CE), will be summarized for the Safety Population by treatment group using descriptive statistics.

## **5.6. Safety – Adverse events**

A treatment-emergent AE (TEAE) is defined as an event that was not present prior to administration of the dose of study drug (ultevursen or sham-procedure) and present after the dose or if it represents the exacerbation of an event that was present prior to the dose.

Adverse events will be summarized by treatment group separately as follows:

- For non-ocular AE:
  - by subject, therefore, in any tabulation, a subject contributes only once to the count for a given adverse event (System Organ Class [SOC] or Preferred Term [PT])
  - and during the overall study period (i.e., up to the last visit for the last subject).

- Time to onset will be calculated in hours, relative to the last dose received, irrespective of which eye received the last dose (i.e., TE or CE).
- For ocular AE:
  - by eye frequencies, separately for the TE and the CE, therefore, in any tabulation, an eye contributes only once to the count for a given AE (by SOC or PT). AEs that are reported in both eyes (i.e., OU) will be reported individually by eye in the tabular summaries.
  - and during the overall study period (i.e., up to the last visit for the last subject).
  - Time to onset will be calculated in hours, relative to the last dose received in the eye experiencing the ocular AE.

Unless otherwise stated, any summary of any type of TEAEs which includes the SOC and PT of the events will order the SOC and the PTs within the SOC by descending incidence of PT.

The following summary tables will be produced separately according to the type of AEs (ocular/non-ocular where applicable) as defined above:

- Overview of Ocular Adverse Events for Treatment Eye during the overall study period (Safety Population)
- Overview of Ocular Adverse Events for Contralateral Eye during the overall study period (Safety Population)
- Overview of Non-Ocular Adverse Events during the overall study period (Safety Population)
- Summary of Ocular Treatment-Emergent Adverse Events for Treatment Eye during the overall study period by MedDRA System Organ Class and Preferred Term (Safety Population)
- Summary of Ocular Treatment-Emergent Adverse Events for Contralateral Eye during the overall study period by MedDRA System Organ Class and Preferred Term (Safety Population).
- SAEs
- AESIs

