2.6 Dose Selection

The target regimen of ultevursen will consist of a loading dose of 180 µg, followed by maintenance doses of 60 µg after 3 months, and at 6 monthly intervals thereafter. The use of a loading dose followed by maintenance doses aims at reaching steady state (efficacious) levels in the retina from the first injection, to maximize clinical response and the potential to provide benefit to the subject. A second arm will test the efficacy and safety of a dose regimen of ultevursen without a high loading dose (i.e., 60 µg loading dose, followed by 60 µg maintenance dose at month 3, and every 6 months thereafter).

As AONs are readily distributed to all eye tissues, and the vitreous is not acting as a drug reservoir, the axial length and overall eye volume are considered the most important parameter for determining the ultevursen dose and the highest recommended IVT injection volume. At around 3 years of age, the human eye is fully developed, and the compartmental volume is 90% of that in adulthood ([Fledelius 2014](#), [Vinekar 2015](#)). The axial length of the eye changes from approximately 16 to 18 mm at birth, 19.5 mm in infants, 23 mm in 3-year-olds, until 22 to 24 mm in adults ([Hellstrom 1997](#)).

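### SAP 5.6 tabulates AEs over the whole study only, so no listed table isolates the interval after the Day 1 dose, the one dose on which the two active regimens differ

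*SAP*

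**What the plan says.** Protocol 2.6 describes the target regimen as a 180 µg loading dose, "followed by maintenance doses of 60 µg after 3 months, and at 6 monthly intervals thereafter". The comparison regimen starts at 60 µg, "followed by 60 µg maintenance dose at month 3, and every 6 months thereafter". SAP 3.1 repeats both schedules with 27 subjects planned per group. Protocol 2.6 also gives the reason for the comparison: "A second arm will test the efficacy and safety of a dose regimen of ultevursen without a high loading dose".

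SAP 5.6 gives ocular and non-ocular AEs the same window: "and during the overall study period (i.e., up to the last visit for the last subject". For ocular events, "an eye contributes only once to the count for a given AE (by SOC or PT". The five fully titled tables repeat the whole-study window, for example "Summary of Ocular Treatment-Emergent Adverse Events for Treatment Eye during the overall study period by MedDRA System Organ Class and Preferred Term". The SAE and AESI entries carry no window in their titles, so the general rule presumably covers them. Time to onset is to be calculated from the most recent dose, but no listed table reports it, and it does not identify which dose that was.

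SAP 6 says that the sponsor stopped the study early, that no formal analysis will be produced, and that tables are limited to disposition, baseline characteristics and an AE overview. By-subject listings, including AEs and study drug administration, are planned in SAP 5.7.

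**The concern.** The randomised difference between the active arms is one injection. A table that runs from Day 1 to the last visit adds events following that injection to events following later, identical ones. With one count per eye per term, a first event many months later weighs the same as one in the week after the 180 µg dose.

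The protocol names the safety of the regimen "without a high loading dose" as something the second arm is there to test, and the AE tables are the only tabulated outcome comparison left. Protocol 2.3 schedules checks one day after injection and again within a week, for endophthalmitis and intraocular inflammation, so the early post-injection period is one the trial itself treats as important. The planned tables cannot show whether such events followed the dose that differed.

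**Working it through.** **Inputs from the documents.** Day 1 dose 180 or 60 µg; common 60 µg dose at Month 3 and every 6 months after (Protocol 2.6, SAP 3.1); 27 per arm planned; 24 months' planned follow-up (Protocol 4.2). Read literally, the schedule puts doses at Day 1 and Months 3, 9, 15 and 21. That is 5 doses, 4 of them identical between the active arms. The interval between the differing dose and the next is 3/24 = 12.5% of planned follow-up.

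**Not in the documents.** Any AE rate, any safety effect size, and the follow-up or number of doses received before the stop. There is no stated figure to reproduce, and everything below rests on assumed rates.

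**Illustration 1: hazard doubled for 3 months only.** Let h be the background hazard per month of a first ocular AE.

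- 60/60 risk by month T: 1 − exp(−hT)
- 180/60 risk by month T: 1 − exp(−[2h×3 + h(T − 3)]) = 1 − exp(−h(T + 3))
- Risk difference: exp(−hT) × [1 − exp(−3h)]

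With h = 0.03:

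| T (months) | 60/60 | 180/60 | Difference (points) | Ratio |
|---|---|---|---|---|
| 3 | 1 − exp(−0.09) = 8.6% | 1 − exp(−0.18) = 16.5% | 7.9 | 1.91 |
| 12 | 1 − exp(−0.36) = 30.2% | 1 − exp(−0.45) = 36.2% | 6.0 | 1.20 |
| 18 | 1 − exp(−0.54) = 41.7% | 1 − exp(−0.63) = 46.7% | 5.0 | 1.12 |

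For h = 0.02 the difference goes from 5.5 points at 3 months (5.8% vs 11.3%) to 4.6 at 12 (21.3% vs 25.9%). For h = 0.05 it goes from 12.0 (13.9% vs 25.9%) to 7.6 (45.1% vs 52.8%). The ratio falls faster than the difference because later background events enter both arms. The difference is the fairer scale.

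**Illustration 2: risk per dose.** Let q be the risk after each 60 µg dose, q1 the risk after the 180 µg dose, doses independent, and k the number of later identical doses.

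- 180/60: 1 − (1 − q1)(1 − q)^k
- 60/60: 1 − (1 − q)^(k+1)
- Difference: (q1 − q)(1 − q)^k, so the proportional loss is 1 − (1 − q)^k

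Starting from a 20-point difference after Day 1:

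| q, q1 | k = 0 | k = 1 | k = 4 | Loss at k = 1 | Loss at k = 4 |
|---|---|---|---|---|---|
| 0.05, 0.25 | 20.0 | 19.0 | 16.3 | 5% | 18.5% |
| 0.10, 0.30 | 20.0 | 18.0 | 13.1 | 10% | 34.4% |
| 0.20, 0.40 | 20.0 | 16.0 | 8.2 | 20% | 59.0% |

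So dilution is slight if most subjects had only one later dose and substantial if they had the full course. A subject stopped before the second dose contributes none.

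**Yardstick.** No test is planned. For scale, at 27 per arm an undiluted 20-point difference in these three scenarios has power of about 0.36 to 0.54 (two-sided 0.05, normal approximation). An early-interval table would therefore also be descriptive.

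**The case against.** The case against is strong on several counts.

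- **The planned tables are legitimate.** Protocol 10.9.1 calls for overall TEAE incidence by treatment group, and the SAP does that. No document promises a by-dose or by-interval table. A reader might infer that the whole-study tables are wrong or biased. They are not: they describe AEs under each randomised regimen as a whole. This stands.
- **No contrast is formally estimated.** SAP 2.2 describes an abbreviated close-out plan, and no between-arm ratio or test is planned. What is diluted is the comparison a reader will make by eye. This stands.
- **Nothing is lost.** The AE and dosing listings allow the split to be rebuilt by hand, and a DMC had safety oversight during the trial. This stands; the gap is one of presentation.
- **The effect may outlast Month 3.** Protocol 2.6 says the loading dose aims at steady-state retinal levels from the first injection, and the lens and retinal changes monitored under Protocol 2.3 need not be early. If the hazard stayed doubled throughout, the 12-month difference at h = 0.03 would be exp(−0.36) − exp(−0.72) = 21.1 points. The whole-study table would then be the more informative one. This is why it must stay.
- **The size is small in eyes.** In Illustration 1, 27 × 7.9%, 6.0% and 5.0% is about 2.1, 1.6 and 1.4 excess eyes.
- **Unequal follow-up between arms.** A reader might infer that the early stop makes the whole-study counts unfair between arms. The documents do not support this: allocation was 1:1:1 (SAP 3.2), the stop was a sponsor decision, and nothing indicates that follow-up differed by arm.
- **The table shells are in a separate document** (SAP 8), not available here. The SAP text itself calls for no split.

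What survives is narrow. The only dose that differs has no table of its own, and supplying one costs little.

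**Conclusion.** The point holds as a cheap reporting improvement. SAP 5.6 has no listed table separating events before the second administration from later ones, although only the Day 1 dose distinguishes the active regimens. If a loading-dose effect on AEs is mainly early, the whole-study tables understate it. The size is unknown. Under a doubled hazard for 3 months on a background of 0.03 per month, the difference falls from 7.9 to 6.0 points at 12 months and 5.0 at 18. Under the per-dose model the loss is 5% to 20% with one later dose and about 18.5% to 59% with four. These figures depend on assumed rates, on the effect ending by Month 3 (or, in the second model, with the first dose), and on how many later doses were given. The planned tables are not invalidated, and no imbalance in follow-up between arms is claimed.

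**What to change.** Keep the whole-study tables. In SAP 5.6 add two outputs for the treated eye, the ocular AE overview and the ocular TEAE table by SOC and PT, as follows:

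- Onset from the first administration to before the second, or to the last visit if no second administration was given.
- By randomised group, naming sham explicitly, because the column order in SAP 5.4 lists the two active groups and all subjects but not sham.
- Number of eyes at risk in each interval.
- The complementary later interval alongside.
- A flag, or separate count, for events whose onset date was imputed. SAP 5.6.1 places completely missing onset dates, and some partial ones, at the first administration. Where only the day is missing in any later month it uses the first of that month, which can move an event to before the second dose. SAP 5.6.1 also limits imputation to identifying TEAEs, so any use of imputed dates to assign an interval must be stated.

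The cost is SAP wording and a few programmed tables from onset and dosing dates already collected. The downside is smaller counts per interval, and the tables remain descriptive.
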